5.1. Handling of Missing Data in Analysis

Up to 3% of subjects have been estimated to drop out prior to end of follow-up before 90 days. Distribution of subjects lost to follow-up and missing data on key variables across the treatment groups will be monitored throughout the study.

Missing endpoint data will not be imputed. All those with missing endpoint data either due to attrition or active withdrawal of consent will be excluded from primary analysis. Those who completed 90 days of follow-up and have initial 90 day blood-draw demonstrating a $\geq 50\%$ increase in serum creatinine but are missing the confirmatory blood draw will not be included in the primary analysis as having met the primary endpoint, however, they will be included in the sensitivity analysis as having met this endpoint data. See section 5.3.5.

5.2. Univariate and Bivariate Distributions of Baseline, Procedure Related, Safety and Follow-up data

- In general, the number of observations, mean, median, standard deviation, minimum, and maximum will be calculated for continuous variables. The number of decimal places will be to plus two decimal places.
- Frequencies and percentages will be calculated for categorical data.
- Distribution of continuous variables and proportions of categorical variables will be tabulated by intervention group, and t-test and chi-square tests will be performed to evaluate if these variables are balanced across 4 intervention groups.
- Baseline is defined as the randomization visit.

5.3. Primary Efficacy Analysis

Primary efficacy analysis will include the intention to treat sample as defined in 3.3 and further specified in 5.1 above.

The primary hypotheses will be tested by modeling the binary outcome of presence or absence of MAKE-D event within 90 days post angioplasty procedure. All the proposed tests for the primary analysis are tests of superiority and will be set up as two-sided tests, i.e., study intervention can be better or worse than the control.

Our analytic strategy is to use generalized linear model regression, specifically the GENMOD procedure in the SAS statistical package with a logit link, to model the binary outcome data to estimate the odds of a MAKE-D event at 90 days post angioplasty among those allocated to IV isotonic sodium bicarbonate therapy compared to those allocated to IV isotonic saline, and among those allocated to NAC compared to those allocated to Placebo. Sample SAS code is provided in section 6.

Analytic reports will provide the proportions, the differences among proportions, the odds ratios, and the 95% confidence interval, Wald chi-square p-value, followed by a report of the results.

5.3.1. Testing for Interaction

A multivariable logistic regression model to be fitted includes two binary predictors with an interaction term, and can be expressed as:

$$\text{Log (Odds (MAKE-D))} = \alpha + \beta_1 X_1 + \beta_2 X_2 + \beta_3 X_1X_2 \quad (\text{Model 1})$$

Where X_1 is the indicator for IV intervention (1=Bicarb, 0=Saline), X_2 is the indicator variable for oral intervention (1=NAC, 0=Placebo), and X_1X_2 is the interaction of the two interventions (1=Bicarb and NAC, 0=otherwise).

The parameter β_1 will estimate the independent effect of Bicarb compared to Saline, the parameter β_2 will estimate the independent effect of NAC compared to Placebo, and the parameter β_3 will estimate the additional effect of both Bicarb and NAC.

Presence of significant interaction between Bicarb and NAC (either beneficial or detrimental) will be tested as follows.

Null	$H_0: \beta_3 = 0$
Alternative	$H_a: \beta_3 \neq 0$

If the Wald Chi-square test has $p > 0.05$, then the null hypothesis for interaction cannot be rejected and we will conclude that there is no evidence of significant modification of effect from receiving both Bicarb and NAC.

If the Wald Chi-square test has $p \leq 0.05$, then the null hypothesis for interaction will be rejected and alternative hypothesis accepted to conclude that a significant modification of

effect exists from receiving both Bicarb and NAC. Primary analysis will proceed as described in section 5.3.3.

5.3.2. Absence of Interaction

In the event of a non-significant interaction term at $p=0.05$ level, the regression model will be refitted without the interaction term. This multivariable logistic regression model will include two binary predictors, and can be expressed as:

$$\text{Log (Odds (MAKE-D))} = \alpha + \beta_1 X_1 + \beta_2 X_2 \quad (\text{Model 2})$$

Where X_1 is the indicator for IV intervention (1=Bicarb, 0=Saline), and X_2 is the indicator variable for oral intervention (1=NAC, 0=Placebo).

The parameter β_1 will estimate the independent effect of Bicarb compared to Saline, and the parameter β_2 will estimate the independent effect of NAC compared to Placebo.

Efficacy of Bicarb relative to Saline will be tested as follows.

Null	$H_0: \beta_1 = 0$
Alternative	$H_a: \beta_1 \neq 0$

If the Wald Chi-square test has $p \leq 0.024$, then the null hypothesis will be rejected and alternative hypothesis accepted. If the 95% Confidence Interval of the Odds Ratio does not include 1 and $\beta_1 < 0$, we can conclude that Bicarb is superior to Saline, after adjusting for NAC and Placebo. Conversely, if the 95% Confidence Interval of the Odds Ratio does not include 1 and $\beta_1 > 0$, we can conclude that Bicarb is not superior to Saline, after adjusting for NAC and Placebo.

Similarly, efficacy of NAC relative to Placebo will be tested as follows.

Null	$H_0: \beta_2 = 0$
Alternative	$H_a: \beta_2 \neq 0$

If the Wald Chi-square test has $p \leq 0.024$, then the null hypothesis will be rejected and alternative hypothesis accepted. If the 95% Confidence Interval of the Odds Ratio does not include 1 and $\beta_2 < 0$, we can conclude that NAC is superior to Placebo, after adjusting for Bicarb and Saline. Conversely, if the 95% Confidence Interval of the Odds Ratio does not include 1 and $\beta_2 > 0$, we can conclude that NAC is not superior to Saline, after adjusting for Bicarb and Saline.

5.3.3. Presence of Interaction

In the event of a significant interaction at $p=.05$ level, a stratified analysis will ensue where logistic models with single binary predictors for different levels of X_1 and X_2 will be refitted as follows

In NAC subgroup:	$\text{Log (Odds (MAKE-D))} = \alpha + \beta_{1a} X_1$	(Model 3)
In Placebo subgroup :	$\text{Log (Odds (MAKE-D))} = \alpha + \beta_{1b} X_1$	(Model 4)
In Bicarb subgroup:	$\text{Log (Odds (MAKE-D))} = \alpha + \beta_{2a} X_2$	(Model 5)
In Saline subgroup:	$\text{Log (Odds (MAKE-D))} = \alpha + \beta_{2b} X_2$	(Model 6)

Where X_1 is the indicator for the IV intervention (1=Bicarb, 0=Saline), and X_2 is the indicator variable for the oral intervention (1=NAC, 0=Placebo).

The parameter β_{1a} will estimate the independent effect of Bicarb compared to Saline among those allocated to NAC, β_{1b} will estimate the independent effect of Bicarb compared to Saline among those allocated to Placebo, β_{2a} will estimate the independent effect of NAC compared to Saline among those allocated to Bicarb, and β_{2b} will estimate the independent effect of NAC compared to Placebo among those allocated to Saline.

The efficacy of Bicarb relative to Saline and NAC relative to Placebo will be tested in each of the 4 subgroups at $p=0.048$ overall.

Based on the parameter estimates, the magnitude and direction of any interaction will be evaluated.

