The power calculation for determining the total sample size depends only on these two main effect hypotheses. This means that the exploratory analyses do not have any associated power analyses. The primary analysis will -firstly test the significance of the interaction term, bicarbonate\*NAC. In the event of a non-significant interaction term at p=0.05 level, the regression model will be refitted without the interaction term. Otherwise, a stratified analysis will ensue where logistic models with single binary predictors for different levels of bicarbonate and NAC will be refitted. We will carry out the primary analysis by means of multivariable logistic regression without adjustment for any additional covariates.

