A total of 7680 subjects recruited from the 33 Veterans Health Administration (VHA) centers are expected to be randomized equally to each of the 4 groups as shown in Table 1 below. An additional 1000 subjects are expected to be enrolled in the 12 non-VHA sites in Australia to augment the data collected in the US.

Table 1. Intervention Groups

	Bicarb	Saline
NAC	Group1: NAC+Bicarb	Group2: NAC+Saline
Placebo	Group3:Placebo+Bicarb	Group4:Placebo+Saline

Compare
NAC vs. Placebo
(Groups 1+2 vs. 3+4)

Compare Bicarb vs. Saline
(Groups 1+3 vs. 2+4)

The primary objective:

As the primary objective, the trial will test two hypotheses:

- (#1) IV isotonic bicarbonate is more effective than saline, and
- (#2) NAC is more effective than placebo

in prevention of major adverse kidney events (need for acute dialysis or 50% increase in serum creatinine at 90 days after angiography) and death (MAKE-D) following coronary and non-coronary angiography. This will be accomplished by comparing the incidence of MAKE-D in groups 1 and 3 combined to groups 2 and 4 combined for hypothesis (#1), and by comparing groups 1 and 2 combined to groups 3 and 4 combined for hypothesis (#2). See **3.5.1**.

Secondary Objective:

The trial will also evaluate the effectiveness of the study interventions for the prevention of 5 individual secondary endpoints (section **3.5.2**) by comparing the treatment groups as in the primary objective. The secondary endpoints are:

- 1)contrast induced acute kidney injury (CIAKI) at day5 after angiography
- 2)death
- 3)major adverse kidney endpoints (MAKE)
- 4)hospitalization with acute coronary syndrome, heart failure, or cerebrovascular accident
- 5)all-cause hospitalization.

Tertiary Objective:

The trial will explore the effectiveness of the study interventions for the prevention of the following outcomes (see **3.5.3**), within one year following coronary or non-coronary angiography by comparing the treatment groups as in the primary objective. The tertiary endpoints are:

- 1) development of end stage renal disease (ESRD), and
- 2) death.

3. Investigational Plan

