These estimations assume no interaction between the two active interventions, are adjusted for an O'Brien-Fleming stopping rule with one interim and one final test of hypothesis, and allow for an overall two-sided type I error of 2.5% for each hypothesis being tested. Hence, each of the interim hypothesis for main effect will be tested at p=0.001 level (allowing for 0.1% Type I error), and each of the final hypothesis for main effect will be tested at p=0.024 level (allowing for 2.4% Type I error).

If an attenuation of effect is present due to interaction between Sodium Bicarbonate and NAC, adjustment to the statistical power for 10% to 50% attenuation are given as follows.

Table 5. Statistical Power in the Presence of Effect Attenuation.

% attenuation from interaction between Bicarbonate & NAC	Rate in Bicarbonate/NAC	Rate in treatment (T) group	Rate in control (C) group	% reduction (C-T)/C	Power
No interaction	5.60 %	6.52%	8.7%	25%	90%
10% attenuation	5.78%	6.62%	8.7%	23.9%	87.5%
20% attenuation	5.97%	6.71%	8.7%	22.9%	84%

30% attenuation	6.15%	6.81%	8.7%	21.7%	79.3%
50% attenuation	6.53%	6.99%	8.7%	19.7%	69.4%

Sample recruitment and subsequent event rates will be summarized and presented to the DMC bi-annually as outlined in section 7 below. These reports will be used for monitoring the progress of the study and any modification to the recruitment schedule or the statistical analysis plan will be at the recommendation of the DMC.

5. Statistical Methods

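### SAP 5.3.3 lets a 5%-level interaction test replace the two primary tests with four stratum tests at 0.048 overall; at 0.012 each, family-wise error is about 6.6% against a stated 5%

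*SAP*

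**What the plan says.** **Error budget.** Protocol XVII.A.2 splits 5% equally between the two interventions. SAP section 4 says the calculations "allow for an overall two-sided type I error of 2.5% for each hypothesis being tested", and spends this as 0.001 at the interim and 0.024 at the end: "each of the final hypothesis for main effect will be tested at p=0.024 level". SAP section 2 defines both hypotheses on pooled groups. Protocol XVII.A.1 bases power on the two main effects only, and SAP 5.6 runs the interim on the main-effects model, assuming no interaction.

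**Decision rule.** Both documents test the interaction first.
- Not significant (protocol XVII.A.1): "In the event of a non-significant interaction term at p=0.05 level, the regression model will be refitted without the interaction term". SAP 5.3.2 then tests each main effect: "If the Wald Chi-square test has $p \leq 0.024$, then the null hypothesis will be rejected and alternative hypothesis accepted".
- Significant (SAP 5.3.1): "Primary analysis will proceed as described in section 5.3.3". There, "a stratified analysis will ensue where logistic models with single binary predictors" (Models 3 to 6), and efficacy "will be tested in each of the 4 subgroups at $p=0.048$ overall".

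Neither document assigns alpha to the interaction test or adjusts for the choice it makes. Protocol XVII.A.2 mentions the test only for its effect on power.

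**The concern.** The data choose which primary tests are run, and the two main-effect tests on their own already use nearly all of the 5%. The four stratum tests are primary in their branch, because SAP 5.3.1 says so, but nothing in the budget pays for them.

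An ordinary multiplicity split does not solve this. Each stratum contrast contains the interaction contrast. A trial that enters the branch by chance already has a large interaction statistic, so at least one stratum effect is already part of the way to significance. At stake are formal efficacy or harm claims in one stratum (bicarbonate in patients given NAC, for example) at an error rate above the one the plan states.

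**Working it through.** **Inputs.** Levels 0.001 and 0.024 (SAP section 4); interaction threshold 0.05 (SAP 5.3.1); interim at half the information, main-effects model only (SAP 5.6); two-sided tests (SAP 5.3); equal allocation to four cells (protocol VII.B). Assumption: global null, large-sample normal statistics.

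**1. The plan's own figure.** 0.001 + 0.024 = 0.025 per hypothesis, and 2 × 0.025 = 0.05. Allowing for the correlation √0.5 between looks, the exact values are 2.44% per hypothesis and 1 − (1 − 0.0244)² = 4.81% for the pair. Without the interaction step the plan keeps its promise.

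**2. Stratum statistics.** Let zB, zN and zI be the final statistics for bicarbonate, NAC and interaction; under the null they are independent. The two bicarbonate stratum statistics are (zB ± zI)/√2, so the larger in absolute value is (|zB| + |zI|)/√2. With critical value c, at least one is significant when

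|zB| > √2·c − |zI|.

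The same holds for NAC.

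**3. At 0.012 per test** (0.048/4): c = 2.512 and √2·c = 3.553. At the edge of the branch, |zI| = 1.96, so |zB| > 1.593 is enough. That has probability 0.111, against 0.024 in the main-effects branch. For either intervention it is 1 − (1 − 0.111)² = 21%, and it rises with |zI|. Averaged over |zI| > 1.96, the chance of at least one false stratum rejection inside the branch is 41% (23% for benefit only).

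**4. Combining the branches, final look.**
- Main-effects branch: 0.95 × [1 − (1 − 0.024)²] = 0.95 × 4.74% = 4.51%
- Stratified branch: 0.05 × 40.9% = 2.04%
- Total: 6.55%; with the interim look, 6.6%

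**5. Other per-test levels, both looks, SAP levels 0.001/0.024.**

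| Stratum test level | Family-wise | Per hypothesis | Benefit only |
|---|---|---|---|
| No interaction step | 4.8% | 2.4% | 2.4% |
| 0.048 | 8.7% | 5.5% | 5.0% |
| 0.024 | 7.6% | 4.4% | 4.1% |
| 0.012 | 6.6% | 3.6% | 3.4% |
| 0.001 | 4.9% | 2.5% | 2.5% |
| 0.0008 | 4.8% | 2.4% | 2.4% |

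At 0.0008 the error inside the branch is 4.8%.

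**6. Binomial check.** Simulated trials with 1,862 patients per cell (7,680 less 3%, divided by four), Wald logistic tests and event rates from 7.6% to 9.95% give 6.55% to 6.59% at 0.012 per test (benefit only 3.40% to 3.41%).

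**7. Protocol boundaries.** Protocol XVII.G gives z = 3.18 and 2.25 (p = 0.0015 and 0.0244). Family-wise and per-hypothesis errors are then 4.94% and 2.50% without the interaction step, 6.7% and 3.6% with 0.012 per test, 5.00% and 2.54% with 0.001, 4.95% and 2.51% with 0.0008, and 4.92% and 2.50% with 0.0007.

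**The case against.** **The 6.6% rests on a reading the SAP does not state.** This stands. The word overall could mean that the four tests together hold 4.8% within the branch, in which case the stated limits are met. But that needs about 0.0008 per test. A statistician given only 0.048 and four tests would divide by four, or use 0.024 or 0.048, and each of these exceeds 5%.

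**The pooled hypotheses are not inflated.** True: the main-effects branch contributes 0.95 × 4.81% = 4.6%, less than without the interaction step. A reader might infer that a false claim on a pooled main effect becomes more likely. The documents do not support that; the added error is in stratum claims. One can argue that these are separate estimands with their own 0.048, but SAP 5.3.1 calls them the primary analysis and neither document gives them a second budget.

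**Only benefit counts as success (protocol XVII.B).** The tests and the 5% are still two-sided. On benefit alone the rise is about one percentage point, from 2.4% to 3.4%. A reader might set 3.4% against 5% and see no problem, but the like-for-like comparator is half of 5%, or 2.5%.

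**Stratifying after a real interaction is defensible, and the rule is prespecified.** Both are true. If the interaction is real, a pooled effect averages unequal stratum effects. Prespecification fixes the rule, not its error rate, and here the level that determines the error rate is missing.

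**Conclusion.** The concern holds, conditionally in size. The documents establish that an interaction test at 0.05 selects the primary analysis, that the full 5% is already assigned to the pooled main effects, and that the stratum tests have no stated per-test level. On the Bonferroni reading (0.012 each), error is about 6.6% family-wise, 3.6% per hypothesis and 3.4% for benefit, against 5%, 2.5% and 2.5%. The two looser readings are worse.

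These figures assume the global null and an interim at half the information. A reader might infer that the plan is committed to a 6.6% error, or that stratified analysis is wrong in itself. Neither follows: the SAP leaves the level open, and a strict enough level keeps the limits. The absolute excess is modest and arises only in the 5% of null trials with a chance interaction. This should be fixed; it does not invalidate the design.

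**What to change.** Either of two changes is enough.

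**(a) Remove alpha from the stratum tests.** In SAP 5.3.1 to 5.3.3 and protocol XVII.A.1, test both Model 2 main effects at 0.024 whatever the interaction result. Report the interaction estimate and the four simple-effect odds ratios with confidence intervals as supportive. This agrees with the pooled hypotheses in SAP section 2, the levels in SAP section 4, the interim model in SAP 5.6 and the power basis in protocol XVII.A.1. It does replace the interaction step that protocol XVII.A.1 prescribes, so both documents must change.

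It also costs power if the interaction is real. With the protocol's complete-attenuation cell rates, the chance of showing a bicarbonate benefit at the final look falls from about 59% (in at least one stratum, 0.012 per test) to 38%; the protocol's own figure for main-effects testing there is 40%. The two percentages refer to different claims, stratum and pooled. At 50% attenuation the figures are 73% and 68%; with no interaction, 91% and 90%.

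**(b) Keep the rule and state the level.** Add the per-test stratum level to SAP 5.3.3. About 0.001 holds both limits at the SAP levels 0.001/0.024. At the protocol's z-values it sits at the limits (5.00% and 2.54%), so use about 0.0008 or slightly lower. This is a one-line change. Under complete attenuation it gives about 43% at a per-test level of 0.001, so most of the apparent advantage of the present rule comes from error that was never budgeted.

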5.3.4. Evaluating Covariate Effects

To explore the possibility of treatment by covariate effects, we will refit the model with a vector of covariates included in the model, expressed as

$$\text{Log (Odds (MAKE-D))} = \alpha + \beta_1 X_1 + \beta_2 X_2 + r[Z] \quad (\text{Model 7})$$

Where, $[Z]$ is the vector of factors indicating disease severity, demographic and anthropomorphic measures, and structural factors such as medical site. Factors identified not to be balanced between the intervention groups in section 5.2 will be evaluated.

Additionally, we will explore the effect of including site as a random effect by extending logistic regression to generalized linear models that treat site as a random effect.

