officer, and the VA privacy officer as needed to ensure that data security and data transfers are handled appropriately.

Retention and destruction of data will be conducted according to CSP operating procedures and federal and local VA regulations. This will include paper and electronic data stored at the local sites, the MAVERIC CSPCC, and at the VA facility housing our servers. Identifiable data will be kept according to CSP policy as outlined in the "CSP Guidelines for the Planning and Conduct of Cooperative Studies."

At the completion of the study, a data set from the study will be banked at the MAVERIC CSP Coordinating Center in a data repository that will be established for research purposes under the oversight of the VA Boston Institutional Review Board. The Data Repository will be established and used in accordance with the Repository Protocol, relevant Standard Operating Procedures, and existing regulations. Data will be made available to appropriately credentialed researchers conducting studies related to the topics explored in this protocol or other health questions in accordance with the Standard Operating Procedures of the Data Repository.

Regarding our collaboration with The George Institute in Australia, as described in Section X.D., study data from the VA and The George Institute will be submitted to MAVERIC CSPCC and analyzed as one combined dataset.

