#### **E. Additional exploratory analyses**

We will explore several other hypotheses related to the binary 90 day MAKE-D outcome:

1. The combination of bicarbonate and NAC (interaction term) is more effective than bicarbonate or NAC alone.
2. (Per Protocol analysis) Bicarbonate, NAC, and their combination reduce the incidence of the primary outcome, MAKE-D, among subjects who received the full dose of bicarbonate.
3. (Per Protocol analysis) Bicarbonate, NAC, and their combination reduce the incidence of the primary outcome, MAKE-D, among subjects who received the full course of NAC.
4. Bicarbonate, NAC, and their combination reduce the incidence of the individual components of MAKE-D, each treated as a separate outcome: death, need for acute dialysis, and persistent decline in kidney function.
5. Bicarbonate, NAC, and their combination reduce the incidence of each of the individual cardiovascular components of the secondary outcome; namely acute coronary syndrome, heart failure, and cerebrovascular accident.
6. Bicarbonate, NAC, and their combination result in a greater reduction in the incidence of MAKE-D outcomes in subjects who develop CIAKI compared to those who do not develop CIAKI.
7. Bicarbonate, NAC, and their combination increase the mean number of days that participants are alive and hospitalization free (hospital free days) in the 90 days after angiography.

8. The benefits of bicarbonate, NAC, and their combination on MAKE-D outcomes are independent of the volume and rate of fluid administration above the minimum values prescribed in the protocol.

This brief list entails a large number of analyses. However, the sample size is large and the implicit hypotheses are highly inter-correlated. Thus, we anticipate that we can use a significance level of 1% ( $p = 0.01$ ) to detect associations of potential clinical importance in these exploratory analyses.

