#### Analytic reports

Analytic reports will provide the proportions, the differences among proportions, the odds ratios, and the 95% confidence intervals for each of the summary statistics. This will be followed by a report of the results of confirmatory analyses. The confirmatory exploratory analyses will add to the basic model, factors related to disease severity, demographic and anthropomorphic measures, and structural factors such as medical site. The regression modeling we shall employ will include a model with treatment by covariate terms to explore the possibility of treatment by covariate effects (that is, exploration of potential subgroup effects). We will test that results vary or do not vary significantly by medical site. Finally we will explore the effect of including site as a random effect by extending logistic regression to generalized linear models that treat site as a random effect.

[figure not shown]
Losses to follow up and missing data

We conservatively estimate that up to 3% of subjects may be lost to follow up before 90 days. The site coordinators will make every effort to locate such subjects including at least three telephone contact attempts and one registered letter. Research staff are permitted to mail a letter to the participant for the purpose of appointment scheduling/reminders or follow-up contact. If such efforts fail and we have no information indicating the outcome for these subjects, then we will exclude them from the primary analysis and then carry out a worst case analysis to confirm the result of the primary analysis.

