3.6. Description of Baseline Data

Demographic details (e.g., age, sex, race, ethnicity, marital status, military service), medical history (e.g., co-morbidities, smoking history), and baseline labs will be evaluated overall, by intervention group, by country (Australia or USA), and by enrollment site.

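### SAP Model 7 is meant to explore treatment-by-covariate effects but has no interaction term, and the by-site test promised in the protocol is not carried into the SAP

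*SAP*

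**What the plan says.** SAP 5.3.4 states the purpose of Model 7: "To explore the possibility of treatment by covariate effects, we will refit the model with a vector of covariates included in the model". The model is log odds(MAKE-D) = α + β1X1 + β2X2 + r[Z], where X1 is bicarbonate v saline, X2 is NAC v placebo, and [Z] is described by classes (disease severity, demographic and anthropomorphic measures, structural factors such as site) with no variable named. The section adds "Factors identified not to be balanced between the intervention groups in section 5.2 will be evaluated", referring to SAP 5.2, where "t-test and chi-square tests will be performed to evaluate if these variables are balanced across 4 intervention groups". It then proposes a further model with site as a random effect.

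Protocol XVII.H (Analytic reports) lists four separate things:

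- models that add covariates to the basic model;
- effect modification: "The regression modeling we shall employ will include a model with treatment by covariate terms to explore the possibility of treatment by covariate effects";
- a by-site test: "We will test that results vary or do not vary significantly by medical site";
- a model with site as a random effect.

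The first and last reach the SAP. The second and third do not. The only product term anywhere in the SAP is bicarbonate by NAC (Model 1, SAP 5.3.1).

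**The concern.** A treatment-by-covariate effect is a difference in β1 or β2 between levels of Z. Model 7 forces β1 and β2 to be the same at every level of Z, so it assumes away the quantity it is said to explore. Site is handled the same way. As a member of [Z], or as a random effect as worded, it lets baseline risk differ between sites but leaves one treatment effect for all of them.

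An analyst who follows the SAP exactly would produce no subgroup estimate and no by-site result. To meet the protocol's commitment, someone would have to choose the factors, the model form and the significance level later, possibly after seeing the data. Subgroup findings produced that way carry little weight.

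**Working it through.** **1. The plan's own figure.** Inputs from Protocol XVII.A.2 and XVII.F: control 8.70%, treatment 6.52%, two-sided α 0.025 per hypothesis, 90% power, equal allocation, 3% loss. The pooled-variance formula for two proportions, n per arm = [z(1−α/2)√(2p̄q̄) + z(0.90)√(p1q1 + p2q2)]² / (p1 − p2)², gives a total of 7,342 at α = 0.025 and 7,406 at the SAP's final-look level of 0.024. The plan states 7,450, and 7,450 / 0.97 = 7,680. The plan's figure is reproduced within 2%. The corresponding odds ratio is (0.0652/0.9348) / (0.087/0.913) = 0.732. Nothing below changes these numbers.

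**2. What Model 7 returns when the effect differs.** Assume N = 7,450, a binary covariate splitting patients 50/50, and relative risks for bicarbonate of 0.50 in one half and 1.00 in the other, an average of 0.75. In 400 simulated trials Model 7 gave a mean odds ratio of 0.731, against 0.732 for a uniform 25% reduction. It also showed Z as a significant main effect in 93% of runs, although Z altered risk only through the treatment. Adding X1·Z detected the difference at p < 0.05 in 97.8% of runs.

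**3. Power of the missing term.** Control risk is 8.7% in both halves (assumed), with 7,450/4 = 1,862.5 patients per cell. The interaction estimate is d = ln OR(second half) − ln OR(first half). Its variance is the sum over the four cells of 1/[n·p(1−p)], z = d/SE, and power = Φ(z − z(1−α/2)) + Φ(−z − z(1−α/2)).

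| Relative risks | Odds ratios | d | SE | z | Power at 5% | Power at 1% |
|---|---|---|---|---|---|---|
| 0.50 v 1.00 | 0.477 v 1.00 | 0.740 | 0.182 | 4.06 | 98% | 93% |
| 0.625 v 0.875 | 0.603 v 0.865 | 0.360 | 0.178 | 2.02 | 53% | 29% |
| 0.70 v 0.80 | 0.681 v 0.785 | 0.143 | 0.177 | 0.81 | 13% | 4% |

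All three rows average to the planned 25% reduction. The first is the most favourable case, because the remaining patients get no benefit at all.

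**4. By-site analysis.** 7,450 / 33 = 226 analysed patients per VA site, 113 per arm, so about 113 × 0.087 = 9.8 control events and 113 × 0.0652 = 7.4 treated events. In simulation (33 sites, a 4:1 range of site sizes, between-site SD of baseline risk 0.3 on the logit scale, all assumed), a homogeneity test at 5% had 15%, 35% or 85% power for a between-site SD of the log odds ratio of 0.2, 0.3 or 0.5. Only large variation between sites would be detected reliably.

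**5. Multiplicity of the remedy.** Four factors by two interventions is eight tests. If they are independent, the chance of at least one false positive is 1 − 0.95⁸ = 34% at 5% and 1 − 0.99⁸ = 8% at 1%.

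**The case against.** The strongest reply is that the protocol already commits to both analyses, that SAP section 1 lists the protocol as a source, calls itself guidelines and requires deviations to be documented, and that all of this work is exploratory, with Protocol XVII.A.1 disclaiming any power analysis for it. Much of that stands. The commitment exists, and primary type I error, sample size and power are untouched. What remains is that the SAP's equation conflicts with its own stated purpose, and that neither document names the factors, the model form or a level for these tests.

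Low power is also a fair point: moderate effect differences and modest site variation would usually be missed. That is a reason to report estimates with confidence intervals, not to leave the model out.

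Some stronger readings are not supported:

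- *Balance tests dictate the adjusted model.* The SAP says imbalanced factors will be evaluated. It gives no rule that puts them into the model, and the classes in [Z] are listed independently. The weakness is that no covariates are fixed in advance.
- *A VA v non-VA comparison of effect was promised and dropped.* The data are to be "analyzed as one combined dataset", and SAP 3.6 says "baseline labs will be evaluated overall, by intervention group, by country (Australia or USA), and by enrollment site". That concerns baseline data. Neither document promises a comparison of the treatment effect.
- *Protocol XVII.E item 8 needs an interaction model in [Z].* It proposes that "The benefits of bicarbonate, NAC, and their combination on MAKE-D outcomes are independent of the volume and rate of fluid administration" above the protocol minimum. Fluid actually given is measured after randomisation, so it does not belong among baseline effect modifiers.
- *The unadjusted primary model is an error.* It is pre-specified and valid, and adjusted models are already planned as exploratory.

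**Conclusion.** The point holds as a mismatch between the SAP and both its own stated aim and the protocol. Model 7 cannot show treatment-by-covariate effects, and the promised by-site test has no counterpart in the SAP. It should be corrected, but a reader should not infer that the primary conclusions are at risk: the two main-effect tests, the 7,680 patients and the 90% power stand as planned.

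The loss is in exploratory information. It is large only if the effect differs strongly between patient types (98% power forgone at 5%, 93% at 1%), moderate for 0.625 v 0.875 (53%, 29%) and slight for 0.70 v 0.80 (13%, 4%). These figures assume a 50/50 covariate, equal control risk in both halves and 7,450 analysed patients. The by-site figures rest on the assumed between-site SDs and site sizes. The mismatch itself rests on no assumption; it can be read from the equation.

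**What to change.** Before unblinding:

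1. In SAP 5.3.4, add models with X1·Z and X2·Z, one factor at a time, for a short fixed list of baseline factors already collected. Examples are diabetes, baseline eGFR, coronary v non-coronary procedure, and inpatient v outpatient status. Report estimates and confidence intervals at a stated level. Protocol XVII.E gives 1% for its exploratory list; say whether that level applies here too.
2. Relabel Model 7 as the covariate-adjusted main-effects model, and name its covariates in advance instead of leaving the choice to the SAP 5.2 balance tests.
3. Add the by-site analysis of Protocol XVII.H, for example a random treatment-by-site slope for each intervention, reported as a between-site SD with its confidence interval.

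The cost is SAP wording and a few extra models on data already collected. The downside is more exploratory tests, which is why the factor list should be short and the level stated. The primary and interim tests do not change.
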